## 5 Trial population

## 5.1 Screening data

Full screening details are contained within the CIP. The following summaries will be presented:

- the number of days spent recruiting;
- the number of patients screened;
- the number of patients recruited;
- the number of patients recruited per day;
- the number of screened patients not recruited and the reason for non-recruitment.

This summary will be provided overall and by each centre.

## 5.2 Eligibility

The trial inclusion and exclusion criteria are specified in the CIP.

## 5.3 Recruitment

A CONSORT diagram will be created, comprising the number of people screened, eligible, consented, randomised, receiving treatment, withdrawing and lost to follow-up, with reasons provided (Figure 2).

[figure not shown]

Figure 2. CONSORT diagram template

## 5.4 Withdrawal/follow-up

The level of consent withdrawal shall be tabulated and classified. Because this study involves implantable devices, patients cannot elect to withdraw from the intervention once it has been administered. Therefore the following types of withdrawal are possible:

- withdraw from the intervention after consent but before surgery;
- withdraw from follow-up but allow data collected to date to be used;
- withdraw from follow-up and withdraw consent for data collected to date to be used;
- lost to contact/follow-up;
- withdraw due to being revised (that is, the device has to be removed);
- patient death.

The classification, timing of and reason for each withdrawal or lost to follow-up shall be tabulated.

### 5.5 Baseline patient characteristics

Patients will be described with respect to age at surgery, sex, hip side being treated, current and historical physical activity, Modified Harris Hip Score, height, weight, both overall and separately for the two randomised groups. In addition, type and size of device shall be recorded once the intervention has taken place. Categorical data will be summarised by numbers and percentages. Continuous data will be summarised by numbers and percentages. Continuous data will be summarised by mean, standard deviation and range if data are normal and by median, interquartile range and range of data are non-normal. Statistical tests shall not be undertaken for baseline characteristics, but the clinical importance of any imbalance between groups will be noted.

## 6 Analysis

## 6.1 Outcome definitions

The primary outcome is "composite clinical success". This is a binary outcome measure. Patients are deemed to have achieved CCS if they meet all of the following criteria at the 24 month timepoint:

- Modified Harris Hip Score  $\geq$ 80.
- No revision or pending revision.
- Acetabular radiolucencies: not in all zones.
- Femoral radiolucencies: not in all zones.
- Absence of subsidence/migration of the acetabular or femoral component >5mm with clinical findings.
- Absence of serious adverse device effect (SADE).

The secondary outcomes are:

- Total activity count (AC), calculated as the total time spent in non-sleep and non-sedentary activity (in minutes per week) and minutes (in bouts of at least 10 minutes) of moderate to vigorous physical activity (MVPA) achieved during a week, as measured by the GENEActiv activity tracker over a period of 14 days. Patients will be asked to wear the GENEActiv for the full 14 days, but some non-wear is expected, so for the individual patient's data to be valid, they must wear the device for at least 2 weekdays and 2 weekend-days, for a minimum of 2/3 of their waking hours on each of those days. Total weekly AC and MVPA will be calculated: [5× mean daily weekday AC/MVPA time + 2× mean daily weekend AC/MVPA time], to standardise across all patients no matter what their wear-time, as long as it meets the minimum requirements.
- Physical performance assessment. This will take the form of 2 assessments (30-second chair to stand (CTS) test and stair climb test (SCT)) recommended by Osteoarthritis Research Society International (OARSI) pre-operatively and at each post-operative time point.
- The UCLA Activity Score. This is a patient reported outcome measure (PROM) and takes the form of a self-administered questionnaire. The patient will score a mark between 1 and 10 pre-operatively (historical activity level), pre-operatively (current activity level) and at each post-operative time point (current activity level).
- Hip Outcome Score (HOS). This is a PROM and takes the form of a self-administered questionnaire focussing on activities of daily living and sports/exercise. The patient will score a mark between 0 and 100 pre-operatively and at each post-operative time point.
- Noise generation. This will be assessed via a self-administered questionnaire that has been developed by the sponsor based on the literature. There is no overall score for the questionnaire, but it does include a single visual-analogue scale (VAS) question that will give a mark between 0 and 10 for each patient at each post-operative time point.

All outcomes will be measured at 6, 12 and 24 months post-operatively. In addition, all (serious) adverse events and (serious) adverse device effects will be recorded as and when they occur.

## 6.2 Analysis methods

Analysis methods for primary and secondary outcomes and subgroup analyses are summarised in Table 1. Outcomes shall be reported for each treatment group. No adjustments will be made for baseline variables. Categorical data will be summarised by numbers and percentages and 95% confidence intervals.

Continuous data will be summarised by mean, standard deviate and range if data are normal and by median, interquartile range and range of data are non-normal.

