#### Table 1. Summary of outcomes and analysis methods

Variable/outcome	Hypothesis	Outcome measure	Method of analysis
Primary: CCS	H1 Implant is non- inferior to THR	% patients achieving CCS	Blackwelder's non- inferiority test
Secondary: physical activity	H1 Implant is significantly better than THR	Average daily minutes of activity and mean bouted daily MVPA, minutes	Student's t-test (normal, equal variance) or Welch's t-test (normal, unequal variance) or Wilcoxon Rank-Sum (non-normal)
Secondary: physical performance assessment	H1 Implant is significantly better than THR	Number of chair stands in 30 seconds Time to perform stair climb test	
Secondary: HOS	H1 Implant is significantly better than THR	HOS Questionnaire	
Secondary: UCLA Activity Score	H1 Implant is significantly better than THR	UCLA Activity Score	
Secondary: safety	N/A	Adverse events and adverse device effects	N/A
Secondary: noise	N/A	Noise questionnaire	N/A
Adjustment for stratification	Odds ratios are equal across sites	% patients achieving CCS	Cochran-Mantel- Haenszel test followed by Woolf's heterogeneity test
Subgroup analysis: Low v High pre-op activity/physical assessment score/UCLA	N/A	Average daily CPM Mean bouted daily MVPA, minutes	Student's t-test or Welch's t-test or Wilcoxon Rank-Sum
Subgroup analysis: Low vs high "historical UCLA" score	-		
Subgroup analysis: male v female	N/A	% patients achieving CCS	Fisher's exact test
Subgroup analysis: small H1 Implants v all THRs	-		
Subgroup analysis: large H1 Implants v all THRs			
Subgroup analysis: H1 Implants v device type in the THR group			
Subgroup analysis: H1 Implants v bearing type in the THR group			

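### The key secondary outcomes are compared without their own pre-operative values or site, which gives up precision the plan could have at little cost

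*SAP*

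**What the plan says.** SAP Section 6.2 is categorical: "No adjustments will be made for baseline variables". It gives no reason. For physical activity, physical performance, HOS and UCLA, Table 1 offers "Student's t-test (normal, equal variance) or Welch's t-test (normal, unequal variance) or Wilcoxon Rank-Sum (non-normal"). All three compare the two arms without covariates.

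Section 6.1 provides for baseline values of four of these outcomes:
- The two performance tests (chair stand and stair climb) are done "pre-operatively and at each post-operative time point".
- UCLA is scored "pre-operatively (historical activity level), pre-operatively (current activity level) and at each post-operative time point (current activity level".
- For HOS, "The patient will score a mark between 0 and 100 pre-operatively and at each post-operative time point".

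For the tracker measures (total activity and bouted MVPA), Section 6.1 mentions no pre-operative recording. Section 5.5 lists "current and historical physical activity" among the baseline characteristics without naming an instrument. Table 1 has a subgroup split by activity before surgery, named alongside the performance score and UCLA.

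Section 3.2 stratifies randomisation by site. Section 4.1.3 takes site into account for composite clinical success only. Under Section 5.5, baseline imbalance is not tested; its clinical importance is only remarked on.

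**The concern.** Section 2.2 makes superiority in physical activity and patient-reported outcomes the key secondary objective, and Section 3.4 says that the number of patients was set by the primary outcome. Precision for these comparisons therefore has to come from the analysis. A patient's function before surgery usually explains part of the function afterwards. Section 6.4 itself expects baseline variables to be prognostic when it plans imputation for the primary outcome.

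Leaving the pre-operative value out keeps that explained variation in the standard error. It also leaves any chance imbalance in the estimated difference, with nothing planned beyond a comment. Leaving site out ignores a factor on which the randomisation was balanced.

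There is a linked weakness in Table 1. The test is picked according to normality and equality of variance, with no stated rule for deciding either. The quantity compared (a mean or a rank ordering) can therefore differ between outcomes and between the planned looks. One pre-specified adjusted analysis per outcome would settle both matters.

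**Working it through.** **Inputs from the SAP.** Section 3.4: 100 patients per arm; bouted MVPA 48 minutes per day with THR (SD 42) and 60 with H1, with 90% power stated; total activity 258 minutes with THR (SD 100), 287 for significance and 338 as the higher scenario. Section 3.5.2: final significance level 0.0412. Section 4.1.1: 5% level, with sidedness not fixed for each outcome; two-sided is used below unless noted.

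**Assumption.** The correlation r between pre-operative and post-operative values is not in the SAP. The values 0.3, 0.5 and 0.7 are shown.

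**The plan's own figures first.**
- Total activity: 258 + 2.0415 × 100 × √(2/100) = 286.9, which matches 287 at the 0.0412 level. Power at 338 minutes is above 99%, as stated.
- MVPA: SE = 42 × √(2/100) = 5.94. Power = Φ(12/5.94 − 1.96) = Φ(0.06) = 52%. It is 49% at 0.0412 and 65% one-sided at 5%. The stated 90% is not reproduced. Sixty minutes is about the bare threshold of significance (59.6 at 5%, 60.1 at 0.0412).

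**With adjustment.** The residual SD is SD × √(1 − r²), so variance falls by r² and the equivalent number per arm is 100/(1 − r²). MVPA power is Φ(12/(5.94 × √(1 − r²)) − 1.96), with 2.0415 in place of 1.96 at 0.0412.

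| r | Fall in variance | Equivalent per arm | MVPA power, 5% | MVPA power, 0.0412 | Power for total activity at 287, 5% |
|---|---|---|---|---|---|
| 0 | 0% | 100 | 52% | 49% | 54% |
| 0.3 | 9% | 110 | 56% | 53% | 58% |
| 0.5 | 25% | 133 | 65% | 61% | 66% |
| 0.7 | 49% | 196 | 81% | 78% | 82% |

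The power columns compare ANCOVA with an unadjusted t-test and come before the Hochberg step. The variance and equivalent-number columns apply to any continuous outcome with that r, including the four with a stated baseline. The SAP gives no SD or target difference for those four, so no power can be calculated for them.

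**Correlation needed for 90% MVPA power.** Solve 12 = (1.96 + 1.2816) × 5.94 × √(1 − r²). Then √(1 − r²) = 0.623 and r is about 0.78.

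**The case against.** **Validity.** Under 1:1 randomisation the unadjusted tests keep their error rate and the estimates are unbiased. Ruling out adjustment is a clear advance choice, and these outcomes are secondary. All of this stands. A reader might infer that the planned comparisons are biased or invalid; nothing in the SAP supports that.

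**Tracker baseline.** A reader might take it as settled that activity was measured with the tracker before surgery. Section 5.5 and the Table 1 subgroup point that way. However, Section 6.1 gives no pre-operative recording for the tracker, and the wording of Section 5.5 would also fit the two UCLA scores. The activity part must therefore stay conditional.

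**Comparator for MVPA.** A mean of 48 with an SD of 42, on a scale that cannot go below zero, suggests skewness, and Table 1 would then lead to Wilcoxon. Simulation with 100 per arm and two-sided 5%, under assumed shapes and r from 0.3 to 0.7, gives no consistent winner:
- Constant 12-minute shift: Wilcoxon power is 78% (gamma) or 92% (lognormal), against 56–78% and 58–76% for ordinary ANCOVA.
- Proportional effect: ANCOVA does better for gamma (45–68% against 36%) and is mixed for lognormal (46–65% against 53%).

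So the rise from 52% is not shown to be a gain over the test that the plan would probably use. Ordinary ANCOVA on the raw scale is not clearly the right replacement for MVPA.

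**Need.** At 338 minutes of total activity, unadjusted power already exceeds 99%. The shortfall for MVPA comes mainly from the 90% statement, which is a separate error.

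What the objection does not answer is why outcomes with a recorded baseline and a known randomisation stratum should be analysed without either.

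**Conclusion.** The point holds as a matter of efficiency. For chair stand, stair climb, UCLA and HOS, the SAP records the pre-operative value, stratifies by site, and then bars the adjusted analysis without giving a reason. The variance given up is 9%, 25% or 49% for assumed r of 0.3, 0.5 or 0.7.

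For total activity and MVPA the same reasoning applies only if a pre-operative tracker recording exists. The size of the gain for MVPA over a rank test is not established.

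It is tempting to conclude that adjustment would restore the stated 90% MVPA power. It would do so only at r of about 0.78, and that figure again assumes an unadjusted t-test as the starting point. The 90% statement needs its own correction.

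**What to change.** - **Chair stand, stair climb, UCLA and HOS.** Replace the sentence in Section 6.2 and the choice of tests in Table 1 by one pre-specified ANCOVA per outcome: post-operative value on treatment, the same outcome's pre-operative value and site, with robust standard errors. Report the adjusted difference with its confidence interval and enter its p-value in the Hochberg procedure.
- **Total activity and bouted MVPA.** State whether the tracker is worn before surgery. If it is, adjust for that value and site; if not, adjust for pre-operative UCLA or performance score, probably with a smaller gain.
- **MVPA.** Name one baseline-adjusted method suited to skewness in advance, such as ANCOVA on a transformed scale or on ranks, instead of choosing the test from the data.
- **Unadjusted tests.** Keep them as sensitivity analyses.

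For the four outcomes with a stated baseline, no new data are needed. The cost is SAP wording, a simple rule for missing baselines (mean or indicator imputation) and slightly more analysis work.

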## 6.3 Additional analyses

Kaplan-Meier (KM) survival analysis shall be carried out on each treatment group, where survival is 1revision (removal of the device). KM survival (with 95% confidence intervals) shall be compared between the groups but no formal statistical analysis will take place.

## 6.4 Missing data

Minimal losses to follow–up for the primary outcome is anticipated. Where there are missing data points for certain variables/outcomes at certain time points, this shall be indicated in results tables. However, if more than 5% of missing data is found for the primary outcome, a sensitivity analysis using multiple imputations and estimating–equation methods will be carried out. Multiple imputation will consider imputation models based on prognostic baseline and post-baseline variables under a missing at random assumption.

## 6.5 Harms

Safety management is described fully in the study protocol. The proportion of patients with AEs, SAEs, ADEs and SADEs will be compared descriptively across treatments and differences assessed for clinical significance but no formal statistical testing will take place.

## 6.6 Statistical software

The analysis will be carried out using the up to date version of SPSS.

## 6.7 Data management plan

There is no data management plan (DMP). All trial data will be entered and stored on the EDC (Castor). No data cleaning will be required.

## 6.8 Trial master file

The CRO will hold the trial master file, including details of the randomisation process and protocol deviations.

#### Table 1. Summary of outcomes and analysis methods

Variable/outcome	Hypothesis	Outcome measure	Method of analysis
Primary: CCS	H1 Implant is non- inferior to THR	% patients achieving CCS	Blackwelder's non- inferiority test
Secondary: physical activity	H1 Implant is significantly better than THR	Average daily minutes of activity and mean bouted daily MVPA, minutes	Student's t-test (normal, equal variance) or Welch's t-test (normal, unequal variance) or Wilcoxon Rank-Sum (non-normal)
Secondary: physical performance assessment	H1 Implant is significantly better than THR	Number of chair stands in 30 seconds Time to perform stair climb test	
Secondary: HOS	H1 Implant is significantly better than THR	HOS Questionnaire	
Secondary: UCLA Activity Score	H1 Implant is significantly better than THR	UCLA Activity Score	
Secondary: safety	N/A	Adverse events and adverse device effects	N/A
Secondary: noise	N/A	Noise questionnaire	N/A
Adjustment for stratification	Odds ratios are equal across sites	% patients achieving CCS	Cochran-Mantel- Haenszel test followed by Woolf's heterogeneity test
Subgroup analysis: Low v High pre-op activity/physical assessment score/UCLA	N/A	Average daily CPM Mean bouted daily MVPA, minutes	Student's t-test or Welch's t-test or Wilcoxon Rank-Sum
Subgroup analysis: Low vs high "historical UCLA" score	-		
Subgroup analysis: male v female	N/A	% patients achieving CCS	Fisher's exact test
Subgroup analysis: small H1 Implants v all THRs	-		
Subgroup analysis: large H1 Implants v all THRs			
Subgroup analysis: H1 Implants v device type in the THR group			
Subgroup analysis: H1 Implants v bearing type in the THR group			

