#### 4.1.2.3 Subgroup analyses

The subgroup analyses described in Table 1 are designed to investigate the sensitivity of the conclusions drawn from the overall analysis, thereby increasing the confidence in the results obtained from the primary analysis and therefore will not be subjected to adjustment for type I error due to multiplicity concerns.

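### The implant-size subgroup rows restrict only the H1 arm, so they are not randomised comparisons and cannot add confidence to the primary result

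*SAP*

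**What the plan says.** Table 1 of the SAP contains two size rows: "Subgroup analysis: small H1 Implants v all THRs" and "Subgroup analysis: large H1 Implants v all THRs". They sit in a block that opens with "Subgroup analysis: male v female" and ends with rows for THR device type and "Subgroup analysis: H1 Implants v bearing type in the THR group". The outcome shown for the block is the percentage of patients achieving CCS, and the only method shown is "Fisher's exact test". No cut-off between small and large is given, and no corresponding THR subgroup is defined.

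Three other sections bear on these rows:

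- Section 5.5 lists sex, height and weight among the baseline characteristics, but says that "type and size of device shall be recorded once the intervention has taken place".
- Section 6.2 states: "No adjustments will be made for baseline variables". Under section 3.2, randomisation is stratified by site only.
- Section 4.1.2.3 says that the Table 1 subgroup analyses probe the sensitivity of the overall conclusion, "thereby increasing the confidence in the results obtained from the primary analysis". On that ground it exempts them from multiplicity adjustment.

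**The concern.** A subgroup analysis keeps the protection of randomisation when the same pre-randomisation criterion selects patients in both arms. Here the criterion selects patients in the H1 arm only, and it is a property of the implant received. Patients with a small H1 implant are a selected part of their arm, while the comparator is the whole THR arm. Any patient characteristic that goes with implant size and also affects CCS enters the contrast as if it were a device effect, and nothing in the plan removes it.

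The test is also mismatched to the purpose. The primary hypothesis is non-inferiority with an 8-point margin (sections 2.1 and 3.3). Fisher's test has a null hypothesis of no difference, so in a small subgroup it will usually be non-significant whether or not the device is inferior there. Section 4.1.2.3 invites the reader to take such a result as reassurance.

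At stake is what the trial reports by implant size and sex. An artefact could be reported as a size effect, or a real deficit passed over.

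**Working it through.** The SAP gives no figure for these rows, so there is nothing of its own to reproduce. Two checks show how far the contrasts could mislead.

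**1. Contrast expected when the devices are identical**

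From the SAP: THR success rate 91%, margin 8 points, 100 patients per arm (section 3.3).

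Assumed, because the SAP gives no such data:

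- the proportion of women, f, is 30%, 40% or 50% in both arms;
- small implants go either to 90% of women and 10% of men, or to 80% of women and 20% of men;
- CCS is lower in women than in men by a gap g of 0, 5 or 10 points;
- overall CCS is 91% in both arms.

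Let s_w and s_m be the proportions of women and men who receive a small implant. Then:

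- share of women among small-H1 patients: w_S = f·s_w / [f·s_w + (1 − f)·s_m]
- share of women among large-H1 patients: w_L = f·(1 − s_w) / [f·(1 − s_w) + (1 − f)·(1 − s_m)]
- small H1 minus all THR = −g·(w_S − f)
- large H1 minus all THR = +g·(f − w_L)

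Worked case with f = 0.30, s_w = 0.90, s_m = 0.10, g = 10 points:

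- w_S = 0.27 / (0.27 + 0.07) = 0.794, so small minus all THR = −10 × (0.794 − 0.30) = −4.9 points.
- w_L = 0.03 / (0.03 + 0.63) = 0.045, so large minus all THR = +10 × (0.30 − 0.045) = +2.5 points.

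Range over all the mixes:

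| Sex gap in CCS | Small H1 − all THR | Large H1 − all THR |
|---|---|---|
| 0 points | 0 | 0 |
| 5 points | −1.5 to −2.5 | +1.0 to +2.0 |
| 10 points | −3.0 to −4.9 | +2.0 to +4.0 |

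In these mixes women make up 63% to 90% of the small-H1 group, against 30% to 50% of the THR arm. The small-H1 group numbers 34 to 50 of 100. If CCS were higher in women, the signs would reverse.

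**2. What a non-significant Fisher result would mean**

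Take a true deficit equal to the margin: 83% in small-H1 patients against 91% in 100 THR patients. Summing the binomial probabilities of every pair of counts whose two-sided Fisher p-value is at most 0.05 gives the exact power:

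| Small-H1 patients (assumed) | Power |
|---|---|
| 30 | 20.5% |
| 40 | 23.8% |
| 50 | 25.0% |

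A size group that is worse by the full margin would thus be non-significant in 75% or more of trials.

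**The case against.** The strongest reply is that the confounding is not shown. The SAP has no data on size by sex or CCS by sex, and no size cut-off. A reader might infer from the size rows that the contrast is confounded by sex and stature as a matter of fact. The documents do not support that, and the bias is zero if CCS depends on nothing related to size. This stands, and it is why the figures above are a range that starts at 0. What does not depend on it is the one-armed restriction by a feature recorded after surgery.

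Other objections stand in part:

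- The row label for sex might be read as a comparison of men with women rather than of treatments. Section 4.1.2.3 ties the subgroups to the overall conclusion, which concerns H1 against THR, so the label may be shorthand for H1 against THR within each sex. It is ambiguous, not demonstrably wrong.
- One might infer that the device-type and bearing-type rows are confounded by site or surgeon. Section 3.3 says only that both bearing types are allowed, and the SAP does not say how they are chosen. These rows do share the one-armed structure.
- The method cells for the size rows are blank in the extracted table. Reading them as merged with the Fisher entry above is plausible, since it is the only method in the block, but it remains a reading.
- The hypothesis entries in this block are blank or not applicable, so no row claims non-inferiority, and the margin was set for the primary comparison. The supporting role comes only from the general sentence in section 4.1.2.3. That sentence covers the Table 1 subgroups without exception and does not call them exploratory.

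**Conclusion.** The point holds in a limited form. Followed as written, the size rows produce non-randomised, unadjusted contrasts that section 4.1.2.3 then offers as support for the primary result. That conclusion comes from the text alone. The size of any distortion is assumption-driven: none without a sex gap in CCS, and at most about 4.9 points with a 10-point gap, which is about 61% of the 8-point margin (4.9 / 8). The power figures rest on an assumed 30 to 50 small-H1 patients.

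A reader might go further and infer that the primary non-inferiority result is itself compromised. It is not: the primary analysis, sample size and key secondary analyses do not use these rows. The change should be made because the size and sex findings could mislead and the correction is cheap.

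**What to change.** - Replace the two size rows with the H1 minus THR risk difference in CCS and its confidence interval, within levels of a pre-operative factor already collected in both arms (sex, and height with stated cut-offs). Add a treatment-by-factor interaction, reported as exploratory.
- State that the male and female row means H1 against THR within each sex.
- If the size, device-type and bearing-type rows are kept, label them descriptive and exclude them explicitly from section 4.1.2.3.
- Do not use Fisher p-values as evidence that results are consistent across subgroups.

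The cost is SAP wording and a few tables; no new data are needed, because section 5.5 already lists sex and height. Intervals will be wider because the THR comparator is also subdivided. The interaction will have low power, so failing to find one will not show consistency either.
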